Clinical evaluation of an automated language transcription and analysis app to assist speech and language therapists with clinical decision making in the evaluation of developmental language disorders

Short Title: The Language Explorer Clinical Evaluation Study

[name]

[name]

[name]

[name]

Version 1: 09/09/20

CO-SPONSORS: North Bristol NHS Trust and Therapy Box

FUNDERS: NIHR i4i Programme

NRES reference:

Chief Investigator of Clinical Evaluation Work Package:

[name] – North Bristol NHS Trust

Chief Investigator of NIHR Grant 200889, which provides the funding for this work and the development of the app, is [name], CEO of Therapy Box.

Clinical Queries

- (1) Does Language Explorer distinguish children with Developmental Language Disorder (DLD) from children who have typically developing language skills?
- (2) Does the Language Explorer identify patterns of performance which distinguish groups of children with DLD?
- (3) What are clinicians' (speech and language therapists) and parents/carers' views of Language Explorer?

Sponsor

North Bristol NHS Trust (employer of Chief Investigator and host for this work)

and

Therapy Box (lead applicant for research grant and developers of Language Explorer).

Funder

NIHR i4i Programme (NIHR200889)

This protocol describes the study and provides information about procedures for entering participants. Every care was taken in its drafting, but corrections or amendments may be necessary. These will be circulated to investigators in the study. Problems relating to this study should be referred, in the first instance, to the Chief Investigator.

This study will adhere to the principles outlined in the NHS Research Governance Framework for Health and Social Care (2nd edition). It will be conducted in compliance with the protocol, the Data Protection Act and other regulatory requirements as appropriate.

Table of Contents

1. Introduction	8
1.1 Background	8
1.2 Rational for Current Work	8
1.3 Patient and Public Involvement	9
2. Participant Entry	10
2.1 Settings	10
2.2 Recruitment	10
3. Objectives	13
4. Design	14
4.1 Type of Study	14
4.2 Data Collection	15
4.3 Procedures for Data Collection	18
5. Data Management	24
6. Data Analysis	25
7. Archiving	26
8. Safety Reporting	26
9. Regulatory Issues	29
9.1 Ethics Approval	29
9.2 Consent	29
9.3 Confidentiality	30
9.4 Indemnity	32
9.5 Sponsor	32
9.6 Funding	32
9.7 Monitoring	32
10. Study Management	33
11. Publication Policy	33
12. References	34
13. Appendices	35

STUDY SUMMARY

TITLE	Clinical evaluation of an automated language transcription and analysis app to assist speech and language therapists with clinical decision making in the evaluation of developmental language disorders (DLD).
DESIGN	This study is a clinical evaluation using a mixed methods research design consisting of analysis of quantitative assessment data and qualitative interview data
AIMS	
(1) Determine whether Language Explorer can distinguish children with DLD from those who have typically developing language(2) Determine whether patterns of performance on Language Explorer can be observed for different groups of children with DLD(3) Understand clinician and parent/carer views of Language Explorer
POPULATION	Children aged 4;0 – 7;11 years who have been identified by a speech and language therapist as having DLD.
CHILD ELIGIBILITY	INCLUSION CRITERIA 
• Children aged between 4;0 and 7;11 years• Children who speak and are exposed to only English in the home• Children who have been identified by a speech and language therapist as having DLD or suspected DLD• Case histories that are unremarkable in terms of birth, overall development and general health

EXCLUSION CRITERIA

- Children with history of significant hearing problems (e.g. sensori-neural hearing loss or use of hearing aids in the case of severe and recurrent otitis media)
- Evidence of structural or neurological disorders (e.g. cleft palate, cerebral palsy, autism)
- Children with significant speech difficulties which impact their intelligibility

DURATION 24 months

Three clinical sites are involved in this study:

Bristol

Local PI: [name]

Clinical Lead in Developmental Language Disorders

Sirona care & health

[name]

[name]

[name]

Email: [contact]

[contact]

Hackney

Local PI: [name]

Speech and Language Therapy Service Manager

Children's Integrated Speech and Language Therapy Service for Hackney and the City

Homerton University Hospital NHS Foundation Trust & Hackney Learning Trust

Email: [contact]

[contact]

Newcastle

Local PI: [name]

Lead Speech and Language Therapist for School-Age Services

Paediatric Speech and Language Therapy

Newcastle upon Tyne NHS Foundation Trust

[name]

[name]

Newcastle upon Tyne

[name]

Email: [contact]

[contact]

1. INTRODUCTION

1.1 BACKGROUND

Approximately 10% of children present with delayed language in the early preschool years. Some children make spontaneous progress while others benefit from advice or interventions by health visitors or speech and language therapists (SLTs). However, a substantial number of children have language delay which continues beyond age 4, at which point they are at risk of long-term difficulties with language development. Children with persisting difficulties may be diagnosed as having a Developmental Language Disorder (DLD). Children with DLD are at substantially increased risk of poor outcomes in education, employment, relationships and mental health. Unfortunately, more than half of children with DLD are not identified and so do not receive any additional support.

1.2 RATIONALE FOR CURRENT WORK

Language sampling provides SLTs with important information about the patient's use of spoken language within a naturalistic communication environment and is considered a cornerstone of clinical practice (Miller, 1996). Such samples inform the design of intervention and the identification of children in need of support. Consistent with previous research into language sampling practices, the main barrier to more detailed language sample analysis is the time needed for transcription.

The primary problem that the Language Explorer will address is the time taken in the process of manually transcribing and analysing language produced by children during language assessment. Currently it takes 30 minutes to collect a sample of language within an assessment session and up to 90 minutes after the session to transcribe and analyse the sample. This is time that SLTs do not have but is nevertheless shown to be essential for planning effective and efficient intervention. The software will reduce the time from 120 minutes to less than 20 minutes. Furthermore, the software can be completed by a speech and language therapy assistant, freeing up the SLT's time further. This will enable SLTs to assess more children, more quickly and free up time for intervention as well as provide detailed data to inform clinical management and outcomes from intervention.

There is currently no technology which enables the transcription and analysis of child language to happen on a mobile app with supported transcription and automated language analysis and which provides a report or scaled score for performance.

We know from our survey of 90 SLTs that 100% of SLTs said they would purchase an app if it cut down on time spent transcribing and analysing language samples. This was confirmed by attendees in our focus group at the Royal College of SLTs as part of the i4i Connect project.

A survey of 257 SLTs in Australia showed that language samples were generally short, often not recorded, and analysed informally, meaning that management decisions are being made on insufficient data. Consistent with previous research into language sampling practices, the main barrier to more detailed language sample analysis is the time needed for transcription (Westerveld and Claessen, 2014). This review also indicated that by transcribing the samples, detailed analysis of children's language performance can be undertaken, allowing for effective goal-setting and assisting in objective progress measuring during and following intervention.

1.3 PATIENT AND PUBLIC INVOLVEMENT (PPI)

The Language Explorer application is being developed with funding from the NIHR i4i programme. The proposed project covered by this ethics application is one stream of work within the awarded grant. In the development of the original grant PPI representation was embedded at all points. This has been maintained in the development of the proposed work covered by this application. Currently, the tool is being used by parents and carers with their children in a citizen science activity which will lead to a normative dataset and provide information on functioning of the tool which will be used to make further developments. Children with language impairments were also supported to complete the app in schools in Bristol and Hackney.

The plans for the clinical evaluation, as described in this protocol, have been reviewed by our PPI partner, the CEO of the Association For All Speech Impaired Children (AFASIC), and amendments made in light of her comments. The protocol has also been reviewed and agreed by the local PIs.

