2. PARTICIPANT ENTRY

2.1 SETTINGS

The evaluation will take place across three clinical sites: Sirona Care and Health (Bristol), City & Hackney NHS Trust and Newcastle Upon Tyne NHS Foundation Trust. The speech and language therapy service delivery model for the three clinical sites varies: Bristol and Hackney have similar care pathways while Newcastle's is different. Some study procedures will therefore vary for Newcastle; details of how will be explained throughout the protocol.

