All SLTs involved in recruitment (excluding those involved just in identification of eligible children) or data collection will complete GCP training prior to their involvement with the study to enable them to receive completed consent forms and collect data at the Language Explorer Assessment Clinics. They will be allocated a unique study ID number which will be used on all study documentation related to them, to maintain confidentiality (see details below re study ID).

Children

SLTs will be asked by their service leads (study PIs) (see Appendix E 'Email to Identifying Clinicians') to identify children from existing caseloads and from those who have been recently discharged (within previous three months) who meet the study criteria. A

recruitment pack containing a cover letter from local service (Appendix F), Participant Information Sheet (Parent; Appendix G), Participant Information Sheet (Child 6 to 7 yrs; Appendix R) and Participant Information Sheet (Child 4 to 5yrs; Appendix S) and Consent Forms for parents/carers (Appendix H) and children (Appendix I) will be sent out to parents/carers of eligible children with a prepaid envelope for return of the consent and assent forms to the PI of the local service. If no response has been received after two weeks, the local SLT site will contact parents by phone or email to ask if they would like more information or if they have decided not to participate. Parents/carers may want to discuss the study prior to their involvement. The Participant Information Sheet includes information on who to contact from the study team at BSLTRU in that event.

Following receipt of the consent and assent forms by the local site, the PI will allocate the child and parent/carer with a unique study ID number which will be used on all study documentation related to them (see details below re study ID). Twenty ID numbers will be provided to each site by the study team at BSLTRU prior to the start of the study. The PI, or one of the SLTs participating in the study, will then contact the parent/carer to thank them for their involvement and invite them to a Language Explorer Assessment appointment. This appointment will take place either remotely or in person on a clinical site - for further details on this, see section on Data Collection below.

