At the start of the assessment, the SLT will take assent from the study child using the 'Child Assent Form' (Appendix J). If the child is too young or unable to tick the boxes themselves, or the assessment is taking place remotely, the SLT will initial the boxes. If a child is felt not to have provided assent, the assessment session will not go ahead.

Eligibility criteria for children

Inclusion criteria:

- Children aged between 4;0 and 7;11 years
- Children who speak and are exposed to only English in the home
- Children who have been identified by a speech and language therapist as having DLD or suspected DLD. (DLD is defined here as having moderate to severe language difficulties, not associated with other conditions but which is likely to affect their

functioning in school/preschool and likely to persist – based on the clinical judgment of a SLT)

- Case histories that are unremarkable in terms of birth, overall development and general health

Exclusion criteria

- Children with history of significant hearing problems (e.g. sensori-neural hearing loss or use of hearing aids in the case of severe and recurrent otitis media)
- Evidence of structural or neurological disorders (e.g. cleft palate, cerebral palsy, autism)
- Children with significant speech difficulties which impact their intelligibility

Parents/Carers

The 'Consent Form (Parents/Carers)' (Appendix H) seeks consent for the parent to participate in a semi-structured telephone interview carried out by the study team following their child's attendance at the Language Explorer Assessment Clinic. During the interview they will be asked about the experience of their child using the Language Explorer. Consent for this will be an optional element; the parent can consent for their child to participate in the study but choose not to consent to themselves being interviewed. Parents/carers recruited to the study will be assigned a separate but related ID number to that of their child. Processes for maintaining security and confidentiality of the parents/carers identifying information will be the same as that for the child described above.

Parent/Carer eligibility:

- Parent/carer of a child meeting the inclusion criteria for this study

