- 4) Parent and SLT interview

All children recruited to the study will be assessed on the Language Explorer app. All children will also have the SLT Clinical Judgement Form completed for them. Where the appointment happens remotely, the child will be assessed on the Q-Interactive version of the Clinical Evaluation of Language Fundamentals following the protocol below. Where it takes place in person in a clinical setting, the child will also be assessed on the Clinical Evaluation of Language Fundamentals (CELF-Preschool 2 UK) following the protocol below.

This means that data from all children in the study will be able to be used to address the first aim of the study – to determine the ability of the Language Explorer app to distinguish children with DLD from those who have typically developing language. The Clinical Judgement Form will also be available for all children to investigate the second aim of determining whether patterns of performance can be observed on the Language Explorer app which fits with needs identified by a SLT. Further investigation of this aim will be carried out using the additional data from the comparator assessment for a subsample.

More details on each type of data are as follows:

1) *Language Explorer*

The Language Explorer is an app which has been developed with funding from the NIHR i4i programme to provide a tool for SLTs to use to assist in assessing children's language abilities. Details of each of the tasks within Language Explorer which children are asked to complete are as follows:

Story Re-Tell:

This task requires the child to listen to a story and then re-tell it to produce a sample of narrative language skill. The story is about a boy and a dog going on an adventure to find some treasure. The story is narrated and contains static pictures which change automatically as the story progresses. The adult will tell the child to first listen to the story whilst looking at the pictures and that it will then be the child's turn to re-tell the story. The child will then listen to the story and then re-tell it using their own words. The app automatically records the child's response and provides an automatic transcription, which is checked and corrected as necessary by the SLT and then used by the app to provide an automatic analysis of the child's expressive language functioning on the story retell task.

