4) SLT and Parent Interviews

An interview schedule will be used to guide qualitative data collection from SLTs and parents/carers, (Appendix O 'Interview Schedule (SLT)' and Appendix P 'Interview Schedule (Parent)').

4.3 PROCEDURES FOR DATA COLLECTION:

The procedures for collecting the data vary for each data type and will be described here:

1) *The Language Explorer*

Each clinical site will collect data from 20 children. Two protocols for collection of Language Explorer data are provided: one for remote facilitation for children aged 6 years 0 months to 7 years 11 months and one for when the app is used in person in the clinical setting for children aged 4 years 0 months to 5 years 11 months.

Remote (ages 6 years 0 months to 7 years 11 months):

Parents will be contacted in advance of the remote appointment by the local SLT and asked to download the Language Explorer app to a compatible device. Wherever possible this will be on a tablet, but if that is not available, the child could be assessed on a mobile phone. At the agreed time for the remote assessment, the SLT will take assent from the child and confirm eligibility and confirm consent as outlined in the consent forms. S/he will then ask the parent facilitating the session to open the Language Explorer app. The SLT will ask the parent to use the child's unique study ID number as their username for the tool. This will ensure that the data can be retrieved by the developers and provided to the local SLT and to the study team at BSLTRU. The parent will then be asked to use the Language Explorer app to collect a language sample from the child using the usual processes involved in the tool (i.e. child hears a story and retells it and then completes comprehension and sentence repetition tasks as described above). The app will record the child's speech as they respond to the stimuli and questions on the tool. For the data to be useful and the child's data to be included in the analysis, the story retell task must be completed as a minimum. The app will use this recording to generate an automated transcription. See Appendix N 'Language Explorer Screen shots' for images taken from the app.

During this, the SLT will observe the process. This is important to facilitate transcription of the recorded sample and for the process of being interviewed by the study team later.

In person in a clinical setting (to include NHS clinics, schools, early years settings) (ages 4 years 0 months to 5 years 11 months):

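### The app has already been used by language-impaired children in two of the three recruitment areas, and the protocol neither screens for nor records earlier use, so some scores may come from repeat attempts

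*Protocol*

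**What the plan says.** Protocol section 1.3 describes use of the app before this study. Of families it says "Currently, the tool is being used by parents and carers with their children in a citizen science activity", and of schools, "Children with language impairments were also supported to complete the app in schools in Bristol and Hackney". It adds that this use will "provide information on functioning of the tool which will be used to make further developments".

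Section 2.1 names the sites: "The evaluation will take place across three clinical sites: Sirona Care and Health (Bristol), City & Hackney NHS Trust and Newcastle Upon Tyne NHS Foundation Trust". Under section 2.2, therapists are to "identify children from existing caseloads and from those who have been recently discharged (within previous three months) who meet the study criteria". The eligibility criteria, in the study summary and in section 2.2, cover age, home language, DLD status and case history. The exclusions are hearing problems, structural or neurological disorders, and, last, "Children with significant speech difficulties which impact their intelligibility". No criterion concerns earlier use of the app.

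Section 4.2 describes one story ("The story is about a boy and a dog going on an adventure to find some treasure"), ten questions about it and ten pre-recorded sentences. It mentions no parallel form.

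Section 4.3 assigns ages 6;0 to 7;11 to remote assessment. Their parents are contacted in advance and "asked to download the Language Explorer app to a compatible device". At the session the therapist asks the parent to open the app and enter the study ID as username. Ages 4;0 to 5;11 are seen in person, on a service iPad with the app already loaded.

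**The concern.** Aim 1 is a known-groups comparison of the clinical sample with the Citizen Science norms (sections 4.1 and 6). It assumes that a clinical score reflects a first encounter with the story, questions and sentences. A child who has met them before may score higher for reasons unrelated to language ability, which would move the DLD group towards the norms.

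The possible exposure is also uneven. School use is tied to Bristol and Hackney and not to Newcastle. The home route is open only to the remote age band. Repeat attempts could therefore add score differences linked to site, or to age and mode of assessment, in the correlation and cluster analyses that serve aim 2.

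A later analysis plan could not repair this. If nobody asks about earlier use at identification or at the appointment, there is no variable to adjust for.

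**Working it through.** The protocol gives no effect size, SD, power or exposure rate, so there is no figure to reproduce. The check has two parts.

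**1. Could an exposed child be enrolled and go unnoticed?**

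- School use in Bristol and Hackney is stated (1.3). Recruitment is from caseloads in those areas (2.1, 2.2), and in-person sessions may themselves be held in schools (4.3).
- Eligibility is confirmed at the start of the appointment (4.3), but that step cannot catch something that is not a criterion.
- The study ID makes the data retrievable and is entered at the session (4.3). Otherwise the app holds birth month and year and the first half of the postcode (9.3). An earlier run might be found from these, but could not be tied to a particular child with confidence.

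So a site following the text would enrol an exposed child as a first-time user, and the data would not reliably show it.

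**2. How much could it matter?**

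From the protocol: 20 children per site at 3 sites, 3 × 20 = 60; Bristol plus Hackney, 2 × 20 = 40, or 40/60 = 67%; normative sample 600.

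Assumed: the share of the sample exposed, f; the practice gain in exposed children, g, in SD units; the true gap between DLD and norms, 0.5 or 1.0 SD.

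*Chance of at least one repeat user among the 40*, if each independently has probability p of earlier use: 1 − (1 − p)^40.

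- p = 1%: 33%
- p = 5%: 87%
- p = 10%: 98.5%

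*Shift in the DLD mean* = f × g.

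- Low: 0.05 × 0.2 = 0.01 SD
- High: 0.25 × 0.5 = 0.125 SD
- Extreme, every Bristol and Hackney child exposed: 0.67 × 0.5 = 0.33 SD
- Remote band alone, if half tried the app at home: 0.5 × 0.2 = 0.10 SD to 0.5 × 0.5 = 0.25 SD, with nothing by this route in the in-person band

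For scale, the standard error of a 60 versus 600 comparison is √(1/60 + 1/600) = 0.135 SD. The 0.125 SD shift is a little under one standard error.

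*Effect on a two-sided 5% comparison*, 60 versus 600, equal variances, all 600 used as comparators, gain in the DLD group only:

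| True gap | f | g | Observed gap | Power without shift | Power with shift |
|---|---|---|---|---|---|
| 0.5 SD | 5% | 0.2 | 0.49 | 0.958 | 0.951 |
| 0.5 SD | 25% | 0.5 | 0.375 | 0.958 | 0.791 |
| 0.5 SD | 67% | 0.5 | 0.167 | 0.958 | 0.233 |
| 1.0 SD | 67% | 0.5 | 0.667 | 1.000 | 0.998 |

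The study is not powered on these terms. The table only shows when the shift would start to matter.

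**The case against.** The strongest reply is that no overlap is shown. Section 1.3 gives no number, ages, dates or diagnoses for the school users. They may fall outside 4;0 to 7;11, fail other criteria or never be approached. A reader might infer that some enrolled children will be repeat users. The text supports only that they may be. A reader might also infer that the material was identical, but section 4.2 describes the study version, section 1.3 foresees further development, and nothing says which version the schools used.

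The home route is likewise only a possibility. The written procedure has the app opened at the therapist's request, under observation. The parent information sheet, the cover letter and the download information are not shown and may already advise against trying the app. That advance download leads to practice cannot be read out of section 4.3.

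The direction of bias is not certain either. Families could also repeat the tasks in the normative sample, which would raise the norms and widen the gap. A gain confined to the DLD group would shrink the difference, so it would not create a false claim that the app discriminates. The sub-scores that section 6 gives as examples, such as utterance length and word types, are not shown to rise on a second hearing.

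Lastly, section 4.1 calls the data exploratory and disclaims sensitivity and specificity.

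These points limit the claim to a possibility of unknown size. They do not remove it. The results are meant to inform whether a fully powered validity study is needed, and an understated difference could mislead that decision. The protocol still provides no means of telling first attempts from repeats.

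**Conclusion.** The point stands as a cheap improvement, not as a demonstrated bias. The protocol reports earlier use of the app by language-impaired children in two of its three recruitment areas, and it lets remote families hold the app before the session. It neither screens for nor records earlier use. Repeat attempts at the same or similar material therefore cannot be ruled out, reliably detected or adjusted for.

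Their most likely effect is to narrow the known-groups difference. This rests on two assumptions: that practice raises scores, and that it does so more in the clinical sample than in the norms. Site-linked and age-linked differences are possible as well.

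The size is unknown. With 5% to 25% exposed and a gain of 0.2 to 0.5 SD, both assumed, the shift is 0.01 to 0.125 SD. That matters little for a true gap of 1.0 SD, and becomes material for a gap near 0.5 SD only towards the top of the range or beyond it.

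**What to change.** 1. Ask about and record earlier use of the app (school, Citizen Science, home) when a child is identified and again when eligibility is confirmed at the appointment. This needs one item on the study form and one line in sections 2.2 and 4.3.
2. State that children who have already completed the tasks are left out of the primary known-groups comparison, with a sensitivity analysis that includes them. Alternatively, exclude them at entry by adding a criterion to the study summary and section 2.2. Recording with a sensitivity analysis loses less information, because an entry exclusion leaves no data on repeat users.
3. In the remote procedure of section 4.3 and in the flowchart, tell parents that the app may be installed but its tasks must not be opened before the session. Have the therapist ask about this at the start.

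The cost is a tick-box, a sentence to parents and possibly a few fewer analysable children, chiefly in Bristol and Hackney. The app can still be downloaded in advance, so no session time is lost to installation.
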